#### **6.1.4. General Consideration for Analyses at Week 56 for the 2-year Radiographic Progression in Spine**

Assessment of 2-year radiographic progression in the spine from baseline in studies RHBV and RHBW to Week 56 (Group A: Visit 9/Group B: Visit 513) in RHBY will be evaluated for the Ixekizumab Structure Population (Ixe-Structure) as defined in Section 6.1.1.

Descriptive statistics will be provided for the 2-year radiographic progression in spine measured by change in modified Stoke Ankylosing Spondylitis Spinal Score (mSASSS), the proportion of non-progressors measured by change in Total mSASSS <2 and mSASSS <=0, respectively, and proportion of patients with no new syndesmophyte will be summarized as well.

Cumulative Probability Plot for change from baseline in mSASSS at year 2 will be provided for each ixekizumab treatment group.

Analysis will be done for Ixekizumab Structure Population who have been treated with ixekizumab for at least 24 months, namely who were initially assigned ixekizumab 80 mg Q4W or Q2W in originating studies and not re-randomized to placebo at Week 24 in RHBY. Data will also be summarized for all patients available.

Additional analysis will be repeated for Ixekizumab Structure Population, and Ixekizumab Structure Population who did not participated in the RW period.

#### **6.1.5. General Considerations for Analyses during the Long-Term Extension Period (Period 3)**

Unless otherwise specified, Period 3 starts at the first injection of study treatment at Week 64 or next injection date after Week 64 if injection date of Week 64 is missing and ends on the date of Week 104 or the ETV before the date of Week 104.

##### **6.1.5.1. Dose Escalation Population**

For the Dose Escalation Population, Period 3 starts at the time of first injection of the escalated dose of ixekizumab 80 mg Q2W and ends on the date of Week 104 or the ETV before the date of Week 104.

Summary statistics will be provided for selected efficacy outcomes (including ASDAS clinically important improvement in disease activity) at each scheduled visit after the escalated treatment. No inferential statistics will be provided.

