## 6. A Priori Statistical Methods

### 6.1. General Considerations

Statistical analysis of this study will be the responsibility of Eli Lilly and Company (hereafter, Lilly). The statistical analyses will be performed using SAS® Version 9.4 or higher.

Continuous data will be summarized in terms of the number of observations, mean, standard deviation (SD), minimum, median, and maximum. The minimum and maximum will be reported to the same number of decimal places as the raw data recorded in the database. The mean and median will be reported to 1 more decimal place than the raw data recorded in the database. The SD will be reported to 2 more decimal places than the raw data recorded in the database. In general, the maximum number of decimal places reported shall be 4 for any summary statistic.

Categorical data will be summarized in terms of number of patients in the analysis population, number of patients providing data at the relevant time point, frequency counts, and percentages corresponding to the appropriate method. Percentages will be presented to 1 decimal place. Percentages will not be presented for zero counts. For condition/event that is gender-specific (as defined by the Medical Dictionary for Regulatory Activities [MedDRA]), the denominator and computation of the percentage will include only patients from the given gender.

Change from baseline will be calculated as: observed postbaseline scores – baseline score.

For selective efficacy measures (including ASAS40 components, BASDAI score), percent improvement will be calculated as  $100 \times (\text{baseline score} - \text{observed scores})/\text{baseline score}$ , unless otherwise specified. If a patient has experienced an improvement, this measure will be positive. If a patient has experienced a worsening, this measure will be negative.

Unless otherwise specified, baseline for effect in efficacy and health outcomes analyses is defined as the last available value before the first dose of study treatment in Period 2 from the originating study and, in most cases, will be the value recorded at Week 0 from the originating study. For safety analysis, baseline is defined as the last available value before the first dose at the start of each analysis period of interest in RHBY. For safety analyses using a baseline period, the baseline period is defined as the entire period, that there is no drug dispensed in, prior to the first injection of the drug in the analysis period of interest.

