### **6.1.3.2. Flare Population**

For patients who experienced a flare (Flare Population), a set of selected key efficacy outcomes at time of flare will be summarized.

For the Flare Population with Retreatment in Period 2, the period starts at the time of first injection of the retreatment of ixekizumab 80 mg Q2W or 80 mg Q4W following the flare and ends on the date of Period 2 defined in Section 6.1.3.1.

Summary statistics will be provided based on the Flare Population with Retreatment for a subset of efficacy outcomes: the proportion of patients who regain response in ASDAS <1.3, ASDAS <2.1, and who achieve/maintain an ASDAS<1.3, ASDAS<2.1, ASAS20, ASAS40, ASAS5/6, ASAS partial remission, ASDAS major improvement and clinically important improvement within 16 weeks after the ixekizumab retreatment for patients who have 16 weeks of retreatment. No inferential statistics will be provided. The Kaplan-Meier estimates of the proportion of patients who first regain response on the variables of interest will be carried out at each retreatment interval (4 weeks, 8 weeks, etc.) up to 40 weeks. If an ongoing patient has not regained response by 16 weeks or Week 64, the patient will be censored at 16 weeks and Week 64, respectively. For time to response through Week 64, if a patient discontinued the study prior to Week 64, the patient will be censored at the date of their last visit during Period 2.

For counting regaining a response, once a patient has a response, the status is cumulative and carried forward. This counting process starts at the first visit when the retreatment is initiated. For counting achieving/maintaining a response, the status may change with time and the status depends on the response at each visit and does not depend on the previous visit.

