##### **6.1.5.2. RW Safety Population**

Unless otherwise specified, for the safety analyses during Period 3, baseline is defined as the last nonmissing assessment prior to the first injection of study treatment in Period 3 (mostly at

Week 64). For TEAEs, baseline is the events ongoing just prior to the first injection of study treatment in Period 3.

Summary statistics will be provided for AEs. No inferential statistics will be provided.

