	Sustained Remission (randomization criterion, evaluate at both Week 16 and Week 20)		If (ASDAS $<1.3$ at Week 16 and ASDAS $<1.3$ at Week 20) or (ASDAS $<1.3$ at Week 16 and ASDAS $<2.1$ at Week 20) or (ASDAS $<2.1$ at Week 16 and ASDAS $<1.3$ at Week 20) then Sustained Remission = 1, otherwise 0.	
		Flare (Primary outcome during Period 2)	If ASDAS $\geq 2.1$ at 2 consecutive visits, or ASDAS $>3.5$ at any visit after randomization during Periods 2 and 3 then Flare = 1, otherwise 0. See Section 6.9.1 for coding regarding Week 24 (V505).	NA

		Time to the 1 st flare (major secondary outcome is during Period 2)	Time to the 1 st flare during the Period is calculated as: $\frac{\text{Date of 1st flare in the analysis period} - \text{date of the randomization at Week 24} + 1}{7}$ Note: if a patient had a flare at an intermittent missing visit using the last non-missing observation carried forward, then Date of 1 st flare = last visit date +28 days for Period 2, Date of 1 st flare = last visit date +84 days during Period 3 for the Combined Periods 2 and 3	NA
		ASDAS inactive disease	Defined as ASDAS <1.3	NA
		ASDAS crp change from baseline	Calculated as: observed ASDAS – baseline ASDAS	NA
		Clinical important improvement	Defined as at least 1.1-unit change in ASDAS from baseline, calculated as above.	
		Major improvement	Defined as at least 2.0-unit change in ASDAS from baseline, calculated as above, or reached the minimum of ASDAS score (0.6361) at postbaseline visit.	
modified Stoke Ankylosing Spondylitis Spinal Score (mSASSS)	A spinal x-ray, plain radiograph of the lateral views of cervical and lumbar spine, measured at both baseline of the originating study and Week 56 in RHBY	Total mSASSS	Sum of the scores of 24 sites, each ranges from 0 to 3: 0 = normal; 1 = sclerosis, squaring or erosion; 2 = syndesmophyte; 3 = bony bridge. The total score ranges from 0-72.	See “mSASSS and MRI Data Programming Guidance” for data coding.
		2-year change in Total mSASSS	Change in Total mSASSS for ixekizumab patients = observed Total mSASSS at Week 56 in RHBY – baseline total mSASSS in originating study	NA (complete data).
		Non-progressor (mSASSS <2)	If change in Total mSASSS <2 then Non-progressor = 1, otherwise 0.	NA (complete data).
		Non-progressor (mSASSS ≤0) – sensitivity analysis	If change in Total mSASSS score ≤0 then Non-progressor = 1, otherwise 0.	NA (complete data).

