		SPARCC enthesitis = 0	Only applies to patients with baseline SPARCC enthesitis >0 to count % of patients having SPARCC enthesitis remission.	Missing if observed value is missing.
Tender Joint Count (TJC)	
The number of tender and painful joints will be determined by examination of 46 joints (23 joints on each side of the patient’s body). The 46 joints are assessed and classified as tender or not tender.
	TJC total score	
Adjusted sum of the pain/tenderness for all 46 joints:
 $\left( \frac{\text{sum of all joints checked to be painful/tender}}{\text{number of evaluable joints}} \right) \times 46$ 
See Appendix 2 for details.
	If more than half of the joint scores are non-evaluable, the total score will be missing.
		TJC change from baseline	Calculated as: observed TJC – baseline TJC	Missing if baseline or observed

				value is missing
		TJC = 0	only applies to patients with baseline TJC > 0 to count % of patients having TJC remission.	Missing if observed value is missing
Swollen Joint Count (SJC)	The number of swollen joints will be determined by examination of 44 joints (22 joints on each side of the patient's body). The 44 joints are assessed and classified as swollen or not swollen.	SJC total score	Adjusted sum of the pain/tenderness for all 44 joints.  $\left( \frac{\text{sum of all joints checked to be swollen}}{\text{number of evaluable joints}} \right) \times 44$  See Appendix 2 for details.	If more than half of the joint scores are not evaluable, the total score will be missing.
		SJC change from baseline	Calculated as: observed SJC – baseline SJC	Missing if baseline or observed value is missing
		SJC=0	Only applies to patients with baseline SJC > 0 to count % of patients having SJC remission..	Missing if observed value is missing
Anterior Uveitis or Uveitis Flares	Eye pain or discomfort, eye redness, blurring of vision, or any other symptoms suggestive of anterior uveitis.	Event of anterior uveitis or uveitis flare	When a patient is diagnosed as anterior uveitis or uveitis flare by an ophthalmologist (for patients with no prior history), or a physician (for patients with prior history), then the Event =1, else=0.	If missing then missing

Abbreviations: Baseline = baseline from the originating study RHBV, RHBW or RHBX; CRP = C-reactive protein; IWRS = Interactive Web Response System; no. = number; NRS = numeric rating scale; Q = question; rad-axSpA = radiographic axial spondyloarthritis.

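### SAP 6.1.5.1 sets no pre-escalation baseline, so its one named outcome can count improvement gained before dose escalation as response after it

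*SAP*

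**What the plan says.** SAP 6.1.5.1 moves the start of the analysis window for escalated patients: "Period 3 starts at the time of first injection of the escalated dose of ixekizumab 80 mg Q2W". Within that window it promises descriptive statistics for "selected efficacy outcomes (including ASDAS clinically important improvement in disease activity) at each scheduled visit after the escalated treatment", and it rules out inferential statistics. It does not say what the improvement is measured from.

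Three other places fill that gap:

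- SAP 6.1 gives the general rule: "Unless otherwise specified, baseline for effect in efficacy and health outcomes analyses is defined as the last available value before the first dose". The value comes from the originating study. The section adds that this, "in most cases, will be the value recorded at Week 0 from the originating study".
- Table RHBY.6.4 (SAP 6.10) describes ASDAS clinically important improvement as "Defined as at least 1.1-unit change in ASDAS from baseline, calculated as above".
- The abbreviations under that table state "Baseline = baseline from the originating study RHBV, RHBW or RHBX".

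The next subsection, 6.1.5.2, does reset the reference for Period 3, but for safety only: "baseline is defined as the last nonmissing assessment prior to the first injection of study treatment in Period 3".

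SAP 6.1.1 calls the dose-escalation summaries exploratory. Table RHBY.6.1 lists them as descriptive, without a placebo or non-escalated comparator.

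**The concern.** Under the protocol (5.1 and 7.4), a patient on 80 mg Q4W may be escalated from Week 64 if the investigator judges that more frequent dosing may help to reach adequate disease control. A reader of a table of improvement after escalation will naturally take it to describe what happened since escalation. With the default baseline, the table describes the whole course since the originating study began. Where Week 0 is the reference and the patient rolled over directly, that is 52 + 64 = 116 weeks or more. For patients who started on placebo or adalimumab (SAP 6.7.1 lists both as initial treatments), it also includes any improvement on those treatments.

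The long-term efficacy analysis will not correct the impression. SAP 6.1.2.2 keeps only the Q4W data of escalated patients, and the mBOCF rule in 6.3.3 carries forward their last pre-escalation value.

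**Working it through.** The plan states no figure for this analysis, so there is none to reproduce. The check applies the plan's definitions.

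**Rule.** Let B be the originating-study ASDAS, E the last value before the first escalated injection, and P a post-escalation value. As written, a patient is improved if B − P ≥ 1.1. Change since escalation is E − P.

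**Consequence.** If B − E ≥ 1.1, the patient meets the criterion before the first escalated dose. The patient keeps that status while P ≤ B − 1.1, and so may worsen by up to (B − E) − 1.1.

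**Simple case (illustrative values).** B = 3.9, E = 2.7.
- Before escalation: 3.9 − 2.7 = 1.2, criterion met.
- P = 2.7: 3.9 − 2.7 = 1.2, improved; change since escalation 0.
- P = 2.8: 3.9 − 2.8 = 1.1, improved; worse by 0.1 since escalation.

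**Case built from the ASDAS formula in Table RHBY.6.4 (illustrative component scores).** The order is back pain, patient global, peripheral pain/swelling, morning stiffness, CRP in mg/L.
- Originating study (7, 7, 5, 6, 10): 0.121×7 + 0.110×7 + 0.073×5 + 0.058×6 + 0.579×ln(11) = 3.72.
- Before escalation (5, 5, 3, 4, 4): 0.121×5 + 0.110×5 + 0.073×3 + 0.058×4 + 0.579×ln(5) = 2.54.
- Improvement already present: 3.72 − 2.54 = 1.18, which is at least 1.1. An unchanged patient counts as improved at every later visit.
- The slack is 1.18 − 1.10 = 0.08. If peripheral pain and stiffness each rise by one point, ASDAS becomes 2.67, the change from the originating study is 1.05, and the patient no longer counts. The carry-over covers no change and slight worsening, not any worsening.

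**With a pre-escalation reference.** An unchanged patient has E − P = 0, below 1.1, and is not counted.

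**How many patients?** The documents give no ASDAS distribution at the originating baseline or at escalation. As a sensitivity check only, assume bivariate normal values, no change after escalation, originating mean 3.5 to 4.2 (SD 0.8), pre-escalation mean 2.1 to 3.5 (SD 0.7) and correlation 0.3 or 0.6. The share counted as improved runs from 5% (means 3.5 and 3.5, correlation 0.6) to 93% (means 4.2 and 2.1, correlation 0.6). With means 3.9 and 2.5 it is 63% to 67%. The range is so wide that it gives no estimate; it shows only that the share depends on values the documents do not contain.

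**The case against.** The best counter-argument is that the deciding text may be redacted. The analysis is exploratory, Table RHBY.6.5 has no row for this population, and the list of tables shows a Table RHBY.6.12 for planned exploratory analyses whose body is blacked out. The default in 6.1 yields to anything specified otherwise, so that table could set another baseline. This stands: the point concerns the readable text, and the fix must be conditional. It is also true that the Table RHBY.6.4 note belongs to a table of primary and secondary outcomes. The default in 6.1 leads to the same reference without it.

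It can also be said that response relative to the originating baseline is a legitimate description, consistent with the long-term analyses, and that no visible objective asks for an escalation effect. That is fair, and is why the originating-baseline version should be kept. It does not help a reader who sees only post-escalation visits and cannot tell how many patients already met the criterion. Other outcomes may be reported too, since the named one is only an example; absolute states such as ASDAS below 2.1 do not depend on baseline.

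A reader might infer that the same fault affects retreatment after flare. For example, a patient flaring at 2.2 from an originating 4.2 already has the 2.0-unit fall for major improvement. The documents do not support treating this as the same fault. SAP 6.1.3.2 summarises selected key outcomes at time of flare. It also reports regaining ASDAS below 1.3 and below 2.1, absolute states that a patient at 2.1 or above does not meet. The improvement endpoints ("ASDAS major improvement and clinically important improvement within 16 weeks after the ixekizumab retreatment") are labelled as achieve/maintain and judged visit by visit, so a maintained improvement is what they are meant to count.

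**Conclusion.** The point holds for the readable SAP. Section 6.1.5.1 restarts the window without resetting the efficacy baseline, so the one named outcome counts as improved after escalation any patient who had already improved by 1.1 or more and has not since lost it. This follows from the stated rules and needs no distributional assumption.

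Its reach is small. It affects the interpretation of one exploratory, descriptive, uncontrolled summary; the primary and major secondary tests are unaffected. It rests on Table RHBY.6.12 not setting a different baseline.

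Two stronger readings are not supported. One is that a known, large share of escalated patients is misclassified. The documents contain neither the ASDAS values nor an ASDAS threshold for escalation, which follows the investigator's judgement. The other is that a corrected baseline would reveal the effect of escalation. With no comparator and patients selected for inadequate control, regression to the mean would remain.

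**What to change.** Unless Table RHBY.6.12 already does so, add to SAP 6.1.5.1 that, for the Dose Escalation Population, change and improvement endpoints are reported against the last nonmissing value before the first escalated injection. Show the originating-baseline version beside it, with response status on that definition at the same pre-escalation point. State that the result describes change since escalation and is not an estimate of an escalation effect.

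For retreatment, no new baseline is needed. In 6.1.3.2, include the ASDAS improvement endpoints among the outcomes already summarised at time of flare.

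The cost is a few added sentences, one derived baseline flag and additional table columns. No new data are needed: the Schedule of Activities collects patient global, BASDAI and CRP, from which ASDAS is built, at every scheduled treatment-period visit. No clinical rule changes.

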##### **6.1.5.2. RW Safety Population**

Unless otherwise specified, for the safety analyses during Period 3, baseline is defined as the last nonmissing assessment prior to the first injection of study treatment in Period 3 (mostly at

Week 64). For TEAEs, baseline is the events ongoing just prior to the first injection of study treatment in Period 3.

Summary statistics will be provided for AEs. No inferential statistics will be provided.

### **6.1.6. General Considerations for Analyses during the Post-Treatment Follow-Up Period (Period 4)**

Period 4 starts at the date of the visit (Group A: Visit 14/Group B: Visit 519) at Week 104 or at ETV and ends at study completion or at the last visit prior to study discontinuation. Safety data collected during Period 4 will be summarized by treatment that the patients are taking prior to entering Period 4.

For the safety analyses during Period 4, baseline is defined as the last nonmissing assessment prior to entering Period 4, that is, on or prior to Week 104 (Group A: Visit 14/Group B: Visit 519), or ETV.

## **6.2. Adjustments for Covariates**

The randomization to treatment groups in Period 2 is stratified by geographic region ([Table RHBY.6.2](#)) and originating study (ie, RHBV, RHBW, and RHBX) as described in Protocol Section 6.2. The geographic regions will be collapsed into 2 levels, Europe versus Non-Europe, for statistical analysis ([Table RHBY.6.3](#)). Unless otherwise specified, all efficacy and health outcomes analysis during Period 2 for the RW ITT population will include geographic region and originating study in the analysis model. In general, when ANCOVA is used for analyses during Period 2 for the RW ITT population, baseline value and Week 24 value will be included as covariates.

The initial country allocations and geographic region classification for countries is shown in [Table RHBY.6.2](#).

**Table RHBY.6.2. Geographic Regions for Stratification**

Geographic Region	Country or Countries
North America	United States, Canada
South America	Argentina, Brazil, Mexico
Eastern Europe	Finland, Hungary, Poland, Romania
Western Europe	Austria, France, Germany, Italy, Netherlands, Spain, United Kingdom
Asia	Japan, Korea, Taiwan
Rest of World	Israel, Russia

**Table RHBY.6.3. Geographic Regions for Statistical Analysis**

Geographic Region	Country or Countries
Europe	Czech Republic, Hungary, Poland, Germany, Netherlands, Finland, France, Italy, Spain, United Kingdom, Austria, Romania
Non-Europe	United States, Canada, Mexico, Argentina, Brazil, Japan, Korea, Taiwan, Israel, Russia

## 6.3. Handling of Dropouts or Missing Data

In accordance with precedent in other Phase 3 axSpA trials (van der Heijde et al. 2006; Inman et al. 2008), the following methods for imputation of missing data will be used.

### 6.3.1. Nonresponder Imputation

Analysis of categorical efficacy and health outcome variables will be assessed using an NRI method. Patients will be considered nonresponders (eg, flare) for the NRI analysis if they do not meet the clinical response criteria or have missing clinical response data at any specified analysis time point. All nonresponders at any specified time point, as well as all patients who discontinue study treatment before the specified analysis time point, for any reason, will be defined as nonresponders. Randomized patients without at least 1 observation will also be defined as nonresponders for the NRI analysis.

### 6.3.2. Modified Nonresponder Imputation

Analysis of categorical efficacy and health outcome variables for long-term ixekizumab treatment analysis will be assessed using an mNRI method. Patients will be considered as nonresponders if they receive retreatment due to a flare or discontinue study drug due to AE (including death) or lack of efficacy. For patients discontinuing study drug for any other reason, the data will be imputed using the multiple imputation (MI) method (as described in Section 6.3.4).

